4. SUBJECT DISPOSITION

4.1. Subject Enrollment and Disposition

A summary of subject enrollment will be provided by randomization status and treatment group for each country, investigator within a country, and overall. The summary will present the number and percentage of subjects enrolled. For each column, the denominator for the percentage calculation will be the total number of subjects analyzed for that column.

A table will be provided to summarize discrepancies in the value used for stratification assignment between the IXRS and the clinical database. The denominator for the percentage of subjects in the stratum will be the total number of randomized subjects. A listing of subjects with discrepancies in the value used for stratification assignment between the IXRS and the clinical database at the time of data finalization will be provided.

The randomization schedule used for the study will be provided as an appendix to the CSR.

A summary of subject disposition will be provided by randomization status and treatment group. This summary will present the number of subjects screened, the number of subjects enrolled, the number of subjects randomized, and the number of subjects in each of the categories listed below:

- All Enrolled Analysis Set
- Safety Analysis Set
- All Randomized Analysis Set
- Full Analysis Set
- Of subjects in the All Enrolled Analysis Set:
 - Completed study drug
 - Did not complete study drug with reasons for premature discontinuation of study drug
 - Completed study
 - Did not complete study with reasons for premature discontinuation of study

For the status of study drug and study completion and reasons for premature discontinuation, the number and percentage of subjects in each category will be provided. The denominator for the percentage calculation will be the total number of subjects in the All Enrolled Analysis Set corresponding to that column. In addition, a flowchart will be provided to depict the disposition.

A by-subject listings of reasons for premature discontinuation of study drug will be provided by subject identification (ID) number in ascending order. A similar listing of reasons for study discontinuation will also be provided.

4.2. Extent of Study Drug Exposure and Adherence

Extent of exposure to study drug will be examined by assessing the total duration of exposure to study drug and the level of adherence relative to the study drug regimen specified in the protocol.

4.2.1. Duration of Exposure to Study Drug

Total duration of exposure to study drug will be defined as last dosing date minus first dosing date plus 1, regardless of any temporary interruptions in study drug administration, and will be expressed in weeks using up to 1 decimal place (e.g., 4.5 weeks).

If the last study drug dosing date is missing or partial (month and year available or only year available), the following rules will be used to impute the last dosing date:

For the purpose of calculating the duration of exposure, the last contact date is the latest clinical visit date (including follow-up phone calls when the site was able to reach the subject), laboratory sample collection date, or vital signs assessment date collected in the study.

If the last study drug dosing date is missing, then the last contact date will be used.

If the last study drug dosing date is partial:

- If the month and year are the same as the month and year of the last contact date (defined as above), then the last contact date will be used.
- If the month and year are earlier than the month and year of the last contact date, the last day of the month (or the last day of the year if only year is available) will be used.
- There should not be any partial dosing date with the month and year later than the month and year of the last contact date.

The total duration of exposure to study drug will be summarized using descriptive statistics and using the number (i.e., cumulative counts) and percentage of subjects exposed through the following time periods: 1 day, 4 weeks, 8 weeks, and every 4 weeks after Week 8. Summaries will be provided by treatment group (for randomized subjects) and overall for the Safety Analysis Set, for Run-in and Randomization Phases separately.

No formal statistical testing is planned.

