5.2.2. Packaging and Labeling

SEL and PTM tablets are packaged in white, high-density polyethylene (HDPE) bottles. Each bottle contains 30 tablets, silica gel desiccant and polyester packing material. Each bottle is capped with a child-resistant polypropylene screw cap fitted with an induction-sealed, aluminum-faced liner.

Study drugs to be distributed to centers in the United States (US) and other participating countries shall be labeled to meet applicable requirements of the US Food and Drug Administration (FDA), European Union (EU) Guideline to Good Manufacturing Practice - Annex 13 (Investigational Medicinal Products), and/or other local regulations.

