6.5. Assessments for Subjects who Reach Kidney Failure While on Study Drug

Subjects who reach kidney failure will be instructed to discontinue study drug, complete the EOT and 30 Day (± 7 days) EOT Follow-up visits, which will include an assessment of eGFR and UACR. Following the 30 Day EOT Follow-up visit, subjects who reach kidney failure will continue on study, followed via remote assessments per Section 6.7.3, but no longer followed for the primary efficacy endpoint.

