6.7. Post End of Treatment Follow-up Assessments

Following permanent study drug discontinuation, subjects should remain on study and continue to attend all subsequent study visits in the same manner as subjects who are still on study drug for full assessments (see Section 6.7.1).

Alternative follow-up visits and assessments have been defined to ensure subjects remain on study through the global study end date. If a subject indicates the assessments or in-clinic visits have become burdensome, an alternative follow-up method should be implemented (see Sections 6.7.2 and 6.7.3).

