6.7.3. Remote Assessments

Subjects who have permanently discontinued study drug, reached kidney failure, or are no longer able to continue to attend clinic visits in-person, and **have not withdrawn full consent** will be asked to continue study participation through remote contact, without in-clinic study visits. Subjects will be contacted approximately every 24 weeks until the global study end date. At a minimum, subjects will be contacted at the global study end date.

Subjects will be contacted via telephone, email, or other contact methods through friends or family. Details regarding discussions via telephone, email, or other contact must be properly documented by the site in the source records, including the responses from the subject. The investigator will make every effort to contact the subject or a close relative or caretaker by phone to collect information. The investigator should show due diligence by documenting in the source documents steps taken to contact the subject (e.g., dates of phone calls, registered letters, etc.).

Follow-up for survival, kidney outcomes, and safety will continue until reasons listed in protocol Section 3.5 are met or until the global study end date.

Information gathered will include:

- Survival status
- Death details, if applicable
- Receipt of kidney transplant
- Dialysis initiation post study drug discontinuation
- AE and SAE collection per protocol Section 7

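### A wholly missing last-dose date is imputed as the last contact date, although subjects who stop drug stay in contact until the global study end, so off-drug time can be counted as exposure

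*SAP*

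**What the plan says.** SAP 4.2.1 treats wholly missing and partial last-dose dates differently.

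- **Wholly missing:** "If the last study drug dosing date is missing, then the last contact date will be used". The section explains that "the last contact date is the latest clinical visit date (including follow-up phone calls when the site was able to reach the subject"), and adds laboratory sample and vital-signs dates. These are taken over the whole study, with no limit to the on-treatment period.
- **Partial:** "If the month and year are earlier than the month and year of the last contact date, the last day of the month" is used, or the last day of the year if only the year is known. If the month and year match those of last contact, last contact is used.

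SAP 3.6.1 refers to 4.2.1 as the rule for a missing last dosing date, and no other rule is given.

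The protocol keeps subjects under observation after drug is stopped:

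- 6.7: "Following permanent study drug discontinuation, subjects should remain on study and continue to attend all subsequent study visits".
- 6.7.2: those who ask for less have limited assessments every 12 weeks.
- 6.7.3, remote follow-up: "Subjects will be contacted approximately every 24 weeks until the global study end date". The section adds: "At a minimum, subjects will be contacted at the global study end date".
- 6.5: subjects who reach kidney failure stop drug and, after the 30 Day EOT Follow-up visit, are "followed via remote assessments per Section 6.7.3, but no longer followed for the primary efficacy endpoint".

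SAP 7.1.6.1 computes the EAIR denominators from first to last dosing date.

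**The concern.** Last contact is a sensible stand-in for the last dose when follow-up ends soon after treatment. In this study it does not. For a subject known to have stopped, the latest visit, sample or call is by design an off-drug contact, possibly at the global study end.

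Three outputs are exposed:

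- the duration-of-exposure summary;
- the EAIR denominators;
- any safety window that closes 30 days after the last dose, such as those for laboratory abnormalities (SAP 7.2.2.1, 7.2.2.2) and liver tests (SAP 7.2.3).

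A fourth is exposed only if the same date also sets on- or off-treatment status: the eGFR sensitivity analyses in SAP 6.1.3, 6.2.2.2 and Appendix 2.

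**Working it through.** The plan gives no figure for this rule, so there is none to reproduce. The check has four steps.

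**1. When the rule gives a wrong date.**

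| Subject with no recorded last-dose date | Last contact falls | Result |
|---|---|---|
| Still on drug at last contact | at or near the last dose | reasonable |
| Lost completely, no later contact | near the last evidence of dosing | reasonable |
| Stopped, full or limited follow-up | at a later off-drug visit, sample or vital-signs date | too late |
| Stopped, remote follow-up | at a later call, possibly at study end | too late |

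Partial dates are held to the known month or year. The wholly missing date has no such bound, although Protocol 3.4 schedules an EOT visit as soon as possible after the decision to stop.

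**2. Over-credit per subject** = week of last contact − week of true last dose, in weeks from randomization. Last contact is taken at Week 48 (minimum planned follow-up), Week 84 (horizon of the primary endpoint, SAP 6.1.1) and Week 168 (last window in SAP Table 3-2, used only as an outer limit).

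| True stop | Contact Week 48 | Contact Week 84 | Contact Week 168 |
|---|---|---|---|
| Week 12 | 36 weeks | 72 weeks | 156 weeks |
| Week 24 | 24 weeks | 60 weeks | 144 weeks |
| Week 36 | 12 weeks | 48 weeks | 132 weeks |

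One remote contact interval alone is 24 weeks (24 × 7 / 30.4375 = 5.5 months).

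**3. Arm level, as an illustration.** Assumptions: 150 subjects; follow-up to Week 84; 43 stop at Week 24 (150 × 28.9% = 43, the SEL 18 mg discontinuation rate of the earlier Phase 2 study, Protocol 1.2.3.2.2); k of these have no last-dose date.

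- True exposure = (107 × 84 + 43 × 24) × 7 / 365.25 = 10,020 × 7 / 365.25 = 192.0 patient-years.
- Added per affected subject = (84 − 24) × 7 / 365.25 = 1.15 patient-years.

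| k | Patient-years added | Increase | EAIR factor, same numerator |
|---|---|---|---|
| 1 | 1.1 | 0.6% | 0.994 |
| 5 | 5.7 | 3.0% | 0.971 |
| 10 | 11.5 | 6.0% | 0.944 |

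This base counts randomized time only. SAP 7.1.6.1 adds everyone's Run-in SEL time to the SEL denominator. For 300 randomized subjects at the minimum of 4 weeks, that is 300 × 4 × 7 / 365.25 = 23.0 patient-years. The SEL base becomes 215.0, and the increase for k = 1 to 10 falls to 0.5%–5.3%.

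**4. Direction of the effect on rates.**

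- *Remote subjects:* Protocol 7.3.1 and 7.3.2 collect AEs and SAEs only through the 30 Day EOT Follow-up period. The extra time carries almost no AE ascertainment, so the rate is diluted.
- *Subjects still attending clinic:* AE collection continues. A later last-dose date adds time and may also bring off-drug events into the window, so the rate can move either way.

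The same rule can also reach the Run-in. SAP 4.2.1 summarizes the phases separately, and SAP 7.1.6.1 counts a placebo-arm subject's SEL exposure up to the last Run-in SEL dose. Read literally, a missing Run-in end date would turn randomized placebo time into SEL exposure.

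**The case against.** The best reply is that the trigger is rare. Day, month and year must all be missing. Protocol 5.3 records dosing in source and eCRF, 9.1.6 makes study drug start and end dates required source data, 6.6 calls for consultation before premature discontinuation, and 9.1.7 provides for queries. That stands: the number affected is unknown and probably small. It does not make the stated rule right when it is used.

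A second reply is that SAP 4.2.1 defines last contact only for computing duration of exposure. But SAP 3.6.1 refers to 4.2.1 without that restriction, and an EAIR denominator is itself an exposure duration.

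Several stronger inferences are tempting, and the documents do not support them:

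- *All later eGFR values of an affected subject are mislabelled.* Remote follow-up lists survival, death details, transplant, dialysis and AEs, but no eGFR (Protocol 6.7.3). Only subjects on full or limited follow-up supply off-drug eGFR throughout. Nor does the SAP say that the imputed date sets on- or off-treatment status.
- *AE rates are always diluted.* Step 4 shows that this is clear only for remote subjects. The AE window in SAP 7.1.5.1 is worded in terms of permanent discontinuation, and its link to the imputed date is not spelled out.
- *One arm is affected more.* This needs missing dates to follow stopping by arm, and nothing shows that they do.
- *Tablet supply gives a firm limit for every date.* Protocol 5.2.2 says "Each bottle contains 30 tablets", but the number of bottles dispensed per visit is not stated. Protocol 5.3.1 allows interruptions, after which tablets last longer. A supply-based cap could cut real exposure or override a recorded month.

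**Conclusion.** The point holds as a limited flaw in the SAP. For a known discontinuer with no recorded last-dose date, the rule places the last dose weeks to many months after drug was stopped. The exposure summary and EAIR denominators are inflated, and windows ending 30 days after the last dose can be lengthened. At 1 to 10 affected subjects per arm, the increase in patient-years is about 0.6% to 6%. That range rests entirely on the assumed count and on the follow-up pattern in step 3.

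Mislabelled off-drug eGFR in the sensitivity analyses is a possibility for subjects on full or limited follow-up, conditional on a link that the SAP does not state. A reader might infer that the trial's main result is at risk. It is not: under SAP 6.1.3 the primary slope analysis uses all observed values regardless of treatment discontinuation.

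**What to change.** Amend SAP 4.2.1 as follows.

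1. **Wholly missing date:** use the earlier of the last contact date and the EOT visit or recorded study drug discontinuation date. Only if neither of the latter exists, use the earlier of last contact and the last dispensing date plus tablets dispensed.
2. **Missing last Run-in SEL date in a randomized subject:** bound it by the day before the first randomized dose.
3. **Partial dates:** keep the recorded month or year, and cap at the EOT or discontinuation date only when that date falls within the recorded period.

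It would also help to state whether the imputed date sets on- or off-treatment status, and to report how many dates were imputed in each arm.

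The cost is a short SAP insertion and a small amount of programming. EOT visits are already scheduled, and tablet counts are already on the accountability CRF (SAP 4.2.2). An EOT-based date may still run slightly past the true last dose, and the supply-based fallback remains approximate after a dose interruption.

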4.2.2. Adherence to Study Drug

In this study, the subjects will orally take 1 tablet of the study drug daily. The total number of tablets administered will be summarized using descriptive statistics.

The presumed total number of tablets administered to a subject will be determined by the data collected on the drug accountability CRF using the following formula:

$$\text{Total Number of Tablets Administered} = \left(\sum \text{No. of Tablets Dispensed} \right) - \left(\sum \text{No. of Tablets Returned} \right)$$

4.2.2.1. On-Treatment Adherence

The level of on-treatment adherence to the study drug regimen will be determined by the total amount of study drug administered relative to the total amount of study drug expected to be administered during a subject's actual on-treatment period based on the study drug regimen.

The level of on-treatment adherence will be expressed as a percentage using the following formula:

$$\text{On-Treatment Adherence (\%)} = \left(\frac{\text{Total Amount of Study Drug Administered}}{\text{Study Drug Expected to be Administered on Treatment}} \right) \times 100$$

Descriptive statistics for the level of on-treatment adherence with the number and percentage of subjects belonging to adherence categories (e.g., {< 75%, ≥ 75 to < 90%, ≥ 90%}) will be provided by treatment group for the Safety Analysis Set.

No formal statistical testing is planned.

A by-subject listing of study drug administration and drug accountability will be provided by subject ID number (in ascending order) and visit (in chronological order).

4.3. Protocol Deviations

Subjects who did not meet the eligibility criteria for study entry but enrolled in the study will be summarized regardless of whether they were exempted by the sponsor or not. The summary will present the number and percentage of subjects who did not meet at least 1 eligibility criterion and the number of subjects who did not meet specific criteria by randomization status and treatment group based on the All Enrolled Analysis Set. A by-subject listing will be provided for those subjects who did not meet at least 1 eligibility (inclusion or exclusion) criterion and enrolled. The listing will present the eligibility criterion (or criteria if more than 1 deviation) that subjects did not meet and related comments, if collected.

A by-subject listing will also be provided for subjects who did not meet at least 1 randomization eligibility criterion and randomized. The listing will present the eligibility criterion (or criteria if more than 1 deviation) that subjects did not meet and related comments, if collected.

Protocol deviations occurring after subjects entered the study are documented during routine monitoring. The number and percentage of subjects with important protocol deviations by deviation reason (e.g., nonadherence to study drug, violation of select inclusion/exclusion criteria) will be summarized by treatment group and randomization status for the Safety Analysis Set. A by-subject listing will be provided for those subjects with important protocol deviations.

4.4. Assessment of COVID-19 Impact

This study was ongoing during the coronavirus disease 2019 (COVID-19) pandemic which has an impact on the study conduct. Some subjects were unable to attend onsite visits due to shelter in place guidelines, site closures, or other reasons. This section describes how special situations due to COVID-19 will be handled in the analysis.

4.4.1. Study Drug or Study Discontinuation Due to COVID-19

A by-subject listing of reasons for premature study drug or study discontinuation due to COVID-19 will be provided.

4.4.2. Protocol Deviations Due to COVID-19

A by-subject listing will be provided for subjects with important protocol deviations related to COVID-19. A separate listing will be provided for subjects with non-important protocol deviations related to COVID-19.

4.4.3. Missed and Virtual Visits due to COVID-19

A summary of subjects affected by the COVID-19 pandemic will be provided for each scheduled study visit by treatment group and overall. For each visit, the summary will present the number and percentage of subjects who missed the visit due to COVID-19 or had a virtual visit due to COVID-19. For each column, the denominator for the percentage calculation will be the total number of subjects in the Safety Analysis Set for that column.

An overall summary of the number and percentage of subjects with missed or virtual visits (e.g., at least 1, with 1, 2, 3 or more visits) due to COVID-19 will be provided by treatment group and overall. The denominator for the percentage calculation will be the total number of subjects in the safety population for that column.

A by-subject listing of subjects with missed or virtual visits due to COVID-19 will be provided by subject ID number in ascending order.

Information regarding missed or virtual visits due to COVID-19 will be collected as free text in the CRF comment fields. The determination of missed or virtual visits due to COVID-19 will be done using Natural Language Processing (NLP) to search the CRF comment fields. A detailed explanation of the algorithm is given in [Appendix 4](#).

4.4.4. Adverse Events Due to COVID-19

AEs of COVID-19 will be included in analyses of AEs if applicable, which will be determined through COVID-19 SMQ narrow search. A by-subject listing of AEs of COVID-19 will be provided if applicable.

4.4.5. Overall Assessment of COVID-19 Pandemic Impact

For subjects affected by COVID-19 infection and/or pandemic while participating in the study, a listing of the following individual COVID-19 related outcome categories will be provided:

- Death due to COVID-19
- Adverse event of COVID-19, as determined by COVID-19 SMQ narrow search
- Hospitalization (using data from AE eCRF) due to adverse event of COVID-19 as defined above
- Tested positive for COVID-19
- Study drug discontinuation due to COVID-19
- Study discontinuation due to COVID-19
- Missed visits due to COVID-19
- Missed key assessments due to COVID-19 (Key assessments are the central lab assessments of serum creatinine and/or serum cystatin C)

In addition, composite broad COVID-19 impact indicator will be derived based on the following individual categories defined above: death, adverse event, hospitalization, tested positive, study drug discontinuation, study discontinuation, missed visits, and missed key assessments.

Composite specific COVID-19 impact indicator will be derived based on death and tested positive.

5. BASELINE CHARACTERISTICS

5.1. Demographics and Baseline Characteristics

Subject demographic variables (i.e., age, sex, race, and ethnicity) and Baseline characteristics (body weight [in kg], height [in cm], body mass index [BMI; in kg/m²], systolic blood pressure, diastolic blood pressure, heart rate, ACEi or ARB medication use, and other variables of interest) will be summarized.

Demographic and Baseline characteristics will be summarized by randomized status, treatment group and overall using descriptive statistics (n, mean, SD, median, Q1, Q3, minimum, and maximum) for continuous variables and using number and percentage of subjects for categorical variables. For Baseline body weight, height, and BMI, descriptive statistics will also be presented by sex in the same table. The summary of demographic data will be provided for the Safety Analysis Set. No formal statistical testing is planned.

A by-subject demographic listing, including the informed consent date, will be provided by subject ID number in ascending order.

